improvement. Since initiation about 1 year ago (~13,000 patients), rates of tobacco screening remain consistently at ~90%, suggesting that our approach has successfully accomplished near-universal tobacco use assessment. The prevalence of current tobacco smoking among ACC patients remains under 10%, suggesting overwhelming volume is not an obstacle to referral. Referral rates to TUTS over the 6 months prior to implementation were 0% (C3I required determination of these data to establish base rates), but rose to 34% across the 6 months following implementation, suggesting that clinician behavior changed.³² Focus group data suggest oncologists accept the professional role and social responsibility of monitoring tobacco use, and that TUTS effectively reduced workflow burdens and eliminated practical barriers to engagement. Nonetheless, clinician referral to TUTS remain highly variable; individual referral rates range from 0% to 100%. High rates of order cancellation (i.e. "opting out" of the default referral) emerged as an important barrier to achieving our goal that all clinicians consistently make TUTS referrals. Subsequent efforts to address this issue, including additional education and leadership encouragement (ACC Director and Medical and Radiation Oncology Division Chairs endorsing TUTS at faculty meeting), reduced opt out rates, yet there remains sizable room for improvement. Work in other areas, such as generic medication prescribing in internal medicine practice, suggests that system changes that use a "default" to target clinical behaviors may have an impact on treatment rates but additional work is needed to overcome clinician biases and help patients engage in treatment.³³ Although our simple pragmatic workflow change moved the needle, the next step is to augment the current approach with additional insights from behavioral economics.³⁴

Additional research has identified targets for intervention. For several years, our group has been engaged in applying insights from behavioral economics to understand physician biases around TUT. Findings from preliminary work examining physician preferences toward TUT

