This study will be the first in the oncology setting to compare effectiveness of nudges to clinicians and patients, both head-to-head and in combination, as implementation strategies to improve TUTS referral and engagement. It builds upon our prior work and targets biases among both clinicians and patients, addressing known barriers to tobacco cessation in this high-risk population. The intervention will be embedded within the EMR and clinician-directed nudges will be designed to minimize interference with established workflow while incorporating attention to the motivation needed to make behavior changes.³⁸ This trial will be conducted across the Implementation Laboratory, including both urban and non-urban sites. Finally, the study shares the innovative elements described elsewhere in this application: the use of rapid-cycle approaches to refine the implementation strategies to be tested and the use of mixed methods approaches to enable new insight into context and mechanisms that underlie effectiveness, scalability, and generalizability to other clinical problems and populations.

CHARACTERISTICS OF THE STUDY POPULATION:

1. Target Population and Accrual:

Recruitment will include projected subject recruitment totals of at least 100 clinicians and at least 900 smokers at 9 sites across Penn Medicine's ACC. The target population includes approximately 2,300 high-risk patients with cancer cared for by approximately 275 medical and gynecologic oncology clinicians at the following hospital and free-standing community practice sites of the Penn Medicine Abramson Cancer Center (ACC), referred to hereafter as the "Implementation Laboratory": Hospital of the University of Pennsylvania (HUP), Pennsylvania Hospital (PAH), Penn Presbyterian Medical Center (PPMC), Chester County Hospital (CCH), Lancaster General Hospital (LGH), Valley Forge Medical Center, Radnor Medical Center, Cherry Hill Medical Center, Voorhees Medical Center, Sewell Medical Center, and Regional Hematology Oncology Associates. The trial will be conducted pragmatically, and patients will accrue as they are seen in follow-up at a participating practice site by an eligible provider; this approach may result in a sample of patient that exceeds 900.

2. Key Eligibility Criteria:

Clinician participants must meet the following criteria for enrollment:

- 1) Currently in practice at an Implementation Lab site (UPHS)

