4. Early Withdrawal of Subjects:

We are requesting a waiver of informed consent, so the option to early withdraw from this study is not applicable for Aims 1 and 2 of this project.

5. Vulnerable Populations:

Children, pregnant women, fetuses, neonates, or prisoners are not being targeted in this research study.

6. Populations vulnerable to undue influence or coercion:

We will not be targeting participants who are likely to be vulnerable to undue influence or coercion. Clinicians employed by Penn may experience undue influence to take part in this study and, as outlined in <https://irb.upenn.edu/sites/default/files/IRB%20SOP%20V.11.1-06.2019-Clean.pdf>, efforts are needed to prevent against this potential. To this end, we will send a formal general notification to all clinicians regarding the proposed study, indicating that it will involve data ascertainment from the EHR, that they can opt out, and that decision to opt out will be confidential.

STUDY DESIGN

Aim 1. We will test optimized implementation strategies in a four-arm pragmatic cluster pilot RCT to test the effectiveness of nudges to clinicians, nudges to patients, or nudges to both in increasing TUTS referral and engagement in cancer patients who smoke, vs. usual care (UC – default referral only). Primary and secondary implementation and effectiveness outcomes, and contextual factors that shape implementation effectiveness, will be captured.

Aim 2. We will explore moderators of effectiveness by analyzing associations with variables available via the EMR and clinician survey.

Study Duration:

The exposure period will be 6 months for all participants, with a 90-day follow-up period to measure persistence of effects after implementation strategies end. The baseline period will be 3 months in length, permitting use of rapid cycle approaches (RCA; meetings with co-investigators [name] and [name] and administrators and clinicians within the

Implementation Lab to refine nudges) during this period to optimize implementation strategies. Study analyses will proceed after the follow-up period has completed.

METHODS

1. Study Measures:

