The Aim 1 primary measure of implementation is penetration (TUTS referral rate), defined as the number of TUTS orders signed, divided by the total number of pended orders (i.e., 1-cancellation rate). Our secondary measures of implementation include: prescription rate, defined as the number of pended orders accompanied by a signed prescription order for any of the seven FDA-approved medications for tobacco cessation, divided by the total number of pended orders; treatment engagement rates (medication), defined as the number of patients who make a pharmacologically-assisted quit attempt using any of the seven pharmacotherapies within 90 days of the initial oncology visit, divided by the total number of referred patients; treatment engagement rate (behavioral), defined as the number of patients who receive a quit-line referral or in-person or telephone cessation counseling, divided by the total number of TUTS-engaged patients; quit attempt rate, defined as the number of TUTS-referred patients who make any quit attempt, divided by the total number of TUTS-referred patients; and abstinence rate, defined as the total number of TUTS-referred patients self-reporting 7-day point prevalence abstinence at a 90-day follow-up assessment, divided by the total number of TUTS-referred patients. Established guidelines state that real-world pragmatic, population-based trials such as this do not require biochemical verification of abstinence and including it could introduce significant bias.⁴² Note, we will continue to monitor assessment rate (defined as the number of times the BPA is answered divided by the total number of times it fires) to ensure the intervention does not negatively impact assessment of tobacco use status by staff collecting vital signs or initially rooming the patients such as nurses, front desk staff, MAs, nursing assistants or technicians(baseline rate=90%).

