This is a pragmatic clinical trial focused on increasing use of TUTS. In all arms, clinicians can still choose what they like and patients can still decide to engage in TUTS or not. We will seek a waiver of informed consent for clinicians and patients. We will identify clinicians at the practice sites and their patients using the EMR. Patients will be required to meet the above outlined eligibility criteria. Clinicians (i.e., the unit of randomization) within each site will be randomized to four arms using variable permuted blocks. To control for confounding due to the fact that a small number of clinicians may potentially treat patients at multiple sites, clinicians will be randomized to arm irrespective of site.

We will use RCA to optimize implementation strategies to ensure face validity and maximum effect. We will focus on optimizing content, messaging, and design. RCA procedures involve design meetings with [name] and [name] and with discussions with administrators and clinicians who are members of our Implementation Lab. Clinicians and patients will be exposed to implementation strategies based on their assigned arm.

2. Study Intervention Phase:

Nudges to Clinicians. We will use the Best Practice Alert functionality within the EMR as our conduit to the point of decision-making. All sites use Epic (Epic Systems Corporation, Verona,

WI) to deliver care, or an interoperable system. Epic BPA deployment is modifiable, as we have done at the ACC (CA016520-41S4) and in primary care (DA045244). Epic currently “fires” a BPA for each new patient presenting to ACC within the check-in and vital sign workflow, requiring that staff collecting vital signs or initially rooming the patients such as nurses, front desk staff, Mas, nursing assistants or technicians assess tobacco use status within the past 30 days and satisfy the alert with one of three possible answers (CA016520-41S4). They then activate the “Order” tab for all patients identified as current smokers (i.e., within the past 30 days), resulting in placement of a pended order for consult to TUTS within the clinical workflow.

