We seek to improve TUTS referral and engagement by overlaying normative framed messages to address clinician and patient biases. Upon opening the Epic Order tab at a patient’s next visit after the screening encounter, clinicians will receive the implementation strategy, placed directly over the order interface. The clinician will be required to “acknowledge” or “opt-out” when presented with the order. Opting-out will require clinicians to acknowledge a reason for opt-out using a checklist or free text.

Nudges to Patients. Patients will receive a message sent through myPennMedicine following establishment of their smoking status (at the screening encounter). In all cases, the message will include information specific to the upcoming appointment with the oncology clinician.

Nudges to both clinicians and patients. Both strategies described above will be used.

Usual care. Clinicians and patients will receive no further interventions beyond usual practice. In early 2019, all Penn Medicine ACC clinicians receive the opportunity to refer to TUTS without nudges.

Message design and testing. Messages will be framed to undermine biases. We will optimize the framing of the messages using rapid-cycle approaches to ensure face validity and maximum effect

3. Data Collection:

The EMR and other Penn Medicine secondary databases (the TUTS program) will be used to collect information on practices, clinicians, and patients. These systems are used to routinely collect this information for patient care. We will also collect data from the census via publicly available datasets. Once collected, data are maintained on password-protected computers. [name], who directs the PENN DMS, will oversee the DMS for this study. ORACLE and MS ACCESS permit real-time data entry, storage, and QA by web-based remote access and scannable forms which increases standardization across personnel. We have >15 years of experience with this DMS for smoking cessation trials. The DMS generates database tables, constructs semantic constraints on fields, and is used for data entry, storage, retrieval, and security. The DMS uses visit dates to describe procedures and measures to be ascertained. The DMS mimics the appearance of CRFs which are completed at each visit. Each visit date is “milestoned” (e.g., completed, scheduled, missed). Clinician data will be ascertained by a survey conducted under a separate IRB protocol and funded by this grant.

4. Genetic Testing:

n/a

5. Use of Deception:

n/a

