For Aim 1, we will analyze all binary outcomes using logistic regression with GEE. The study design is factorial, and models will contain binary predictor terms for clinician and/or patient prompt. We will conduct stratified analyses by MPM access. We will also include adjustments for time in months, fixed effects for site, and random effects for clinician. We will control for type 1 error inflation by hierarchical testing, starting with the overall model significance, followed by effect of clinician prompting, followed by patient prompting. Once we have fitted the main effects model, we will test for interaction between clinician and patient prompts, and retain that interaction term if significant (alpha=5%). For Aim 2, variability in these outcomes by treatment arm and moderators will be assessed using interaction terms within logistic regression models. We will fit an adjusted logistic regression model using the same approach described in the primary analysis. Covariates of interest available through the EMR and clinician survey will be added to the model, including patient-level (e.g., cancer type), clinician-level (e.g., years in practice), practice-level (e.g., community vs. hospital-based), and ecological data.

RISK/BENEFIT ASSESSMENT:**1. Risks:**

There are minimal risks to participants in this trial. Regardless of nudges, treatment provided is FDA approved, clinicians routinely order treatment as part of their standard of care, and patients routinely use these smoking cessation treatments. The interventions could increase the time spent discussing smoking cessation with patients. However, shared-decision making is a high priority and evidence-based practice for cancer care and increased time on this topic is likely valuable. In our prior studies, nudges in the EMR were associated with minimal burden on practice staff and clinicians. There is a risk of breach of data and confidentiality, however we described the precautions in place to securely manage this data in the "Data Management" section of this protocol.

2. Benefits:

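### The primary model omits each clinician's pre-trial signed/pended referral rate, a pre-randomisation measure of the primary outcome on the randomised unit, and so gives up some precision

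*Combined protocol and SAP*

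**What the plan says.** - **Model** (Study Procedures, 6. Statistical Analysis). Binary outcomes are analysed by logistic GEE with binary terms for the clinician and patient prompts. Then: "We will also include adjustments for time in months, fixed effects for site, and random effects for clinician". No other covariate enters the primary model.
- **Outcome** (Methods, 1. Study Measures). The referral rate is "defined as the number of TUTS orders signed, divided by the total number of pended orders".
- **Randomised unit** (Study Procedures, Detailed Description). "Clinicians (i.e., the unit of randomization) within each site will be randomized to four arms using variable permuted blocks". Stratification on earlier referral behaviour is not mentioned.
- **Earlier data** (Background; Study Intervention Phase). The default order predates the trial: "In early 2019, all Penn Medicine ACC clinicians receive the opportunity to refer to TUTS without nudges". The Background reports that "individual referral rates range from 0% to 100" per cent, so clinician-level rates have already been computed. It also says that later efforts "reduced opt out rates, yet there remains sizable room for improvement".
- **Baseline period** (Study Duration). "The baseline period will be 3 months in length". Its only stated use is refining the nudges.
- **Aim 2 measures** (Methods, 1. Study Measures). The clinician-level list covers site, years in practice, panel size, smoking prevalence in the panel and type of oncologist. Prior referral rate is absent.

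**The concern.** Treatment varies only between clinicians, so the standard error of a prompt effect depends on how much clinicians differ from one another. An exchangeable working correlation or a clinician effect carries that variation into the standard error; it does not explain any of it. Month and site explain only temporal and between-site differences. A clinician's own earlier rate on the same behaviour can explain part of what remains, and it is fixed before randomisation.

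What is at stake is efficiency. Randomisation with cluster-robust errors already covers chance imbalance in baseline rates between arms. But main-effect power on the plan's own inputs sits slightly under 80%, so a few points are worth having if they are cheap.

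**Working it through.** **Inputs from the plan (Statistical Analysis):** 900 patients, 100 clinicians (m = 9 each), exchangeable correlation ρ = 0.07, 34% versus 45%, two-sided 5%.

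**Assumptions, not in the documents:** prior orders per clinician m_b, and the correlation c between a clinician's underlying rate before and during the trial. At the plan's volume of 900 a year over 100 clinicians, 12 months gives m_b = 9 and 3 months gives 2.25. I take c from 0.5 to 1.

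**Step 1: the plan's own figure.** Design effect = 1 + 8 × 0.07 = 1.56. With n per side, V = (0.34 × 0.66 + 0.45 × 0.55)/n × 1.56 = 0.4719 × 1.56/n, and power = Φ(0.11/√V − 1.96).
- Usual care versus one nudge arm, n = 225: √V = 0.0572, power 48.5%. The plan states 80% for this comparison; it does not reproduce.
- Factorial main effect, n = 450: √V = 0.0404, power 77.6%.

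A pooled null variance gives 48.0% and 77.3%.

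**Step 2: share of clinician-mean variance explained.**

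R² = c²ρ² / {[ρ + (1−ρ)/m_b][ρ + (1−ρ)/m]}

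For m_b = 9, c = 0.8: 0.64 × 0.0049/(0.1733 × 0.1733) = 0.104. That is worth 1/(1 − 0.104) = 1.12, or about 12% more clinicians.

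**Step 3: power with V replaced by V(1 − R²).**

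| m_b | c | R² | Main-effect power |
|---|---|---|---|
| 2.25 | 0.5 | 0.015 | 78.2% |
| 2.25 | 0.8 | 0.037 | 79.2% |
| 2.25 | 1 | 0.059 | 80.0% |
| 9 | 0.5 | 0.041 | 79.3% |
| 9 | 0.8 | 0.104 | 82.0% |
| 9 | 1 | 0.163 | 84.4% |

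Over the same range, the single-arm comparison goes from 48.5% to between 49.1% and 55.7%.

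**Step 4: simulation.** Beta-distributed clinician rates, Poisson panel sizes, exchangeable GEE with robust errors, 4,000 runs per setting:

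| m_b, c | Main effect, without → with | Single arm, without → with |
|---|---|---|
| 2.25, 0.5 | 74.6% → 75.0% | 45.2% → 44.8% |
| 2.25, 1 | 75.4% → 77.1% | 44.7% → 46.3% |
| 9, 0.5 | 73.8% → 75.4% | 45.0% → 45.2% |
| 9, 0.8 | 76.4% → 80.4% | 45.0% → 49.3% |
| 9, 1 | 75.0% → 82.6% | 46.1% → 51.6% |

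**Step 5: more clinicians.** Target Population and Accrual names "approximately 275 medical and gynecologic oncology clinicians". If 900 patients spread over 275, m = m_b = 3.27 and the design effect is 1.159. R² is then 0.010 to 0.039, and main-effect power goes from 88.4% to between 88.7% and 89.6%.

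**Step 6: does the 0% to 100% range imply a larger correlation?** No. Under a beta-binomial with mean 0.34, correlation 0.07 and 4 patients each, 100 clinicians include at least one at 100% with probability 0.93 (0.72 with 5 patients), and at least one at 0% with probability above 0.99. If the correlation were nonetheless larger, so would be the gain: at an assumed 0.25 with 4.5 prior orders, R² is 0.11 to 0.45.

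**The case against.** The strongest reply is that nothing in the plan is wrong: the analysis is valid as written, and one more prognostic covariate is a preference whose value rests on two figures the documents do not give.

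The documents also offer reasons to expect an imperfect link between periods. Opt-out rates changed after the early months. The existing alert fires for new patients, whereas the trial outcome is scored at a later visit. Newly joined clinicians have little or no history. Clinician nudges aim to change this very behaviour. At the weak end (2.25 prior orders, c = 0.5) the simulation shows no gain beyond Monte Carlo error of about 0.7 to 0.8 points. Site effects are already in the model, while the calculations above have no site term, so they may overstate the gain.

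Sample size may matter more. On the same formula, 110 clinicians with 9 patients each reach 81% for the main effect with no covariate. If all of the roughly 2,300 patients named in the target population accrued over 275 clinicians, power would be 99% for the main effect and 88% for a single arm.

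All of this stands as a limit on the size of the gain. It does not show that the information is absent or costly to use. Nor does heavy shrinkage count against it: a clinician with 9 prior orders gets 60% weight on the overall rate (13.3/22.3), which is the appropriate weighting at a correlation of 0.07 and keeps the information that is there.

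**Conclusion.** The point holds as a worthwhile improvement, not a validity problem. The primary model leaves out a pre-randomisation measure of the primary outcome on the randomised unit, although it can be derived from orders already held. With 100 clinicians and a correlation of 0.07, the variance reduction is 1.5% to 16%, depending on prior order volume and stability over time. Main-effect power gains from under one point to about seven. It would be smaller with many more clinicians or where site already explains the differences, and larger if the true correlation exceeds 0.07. The shortfall for usual care versus a single nudge arm is a separate problem that this covariate does not solve.

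**What to change.** Before outcomes by arm are seen, prespecify one covariate in the primary GEE:

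- **Window.** Each clinician's signed and pended TUTS orders over the 12 months ending the day before randomisation or nudge start, whichever is earlier.
- **Sparse histories.** Use (signed + s × overall rate)/(pended + s), with s = (1 − 0.07)/0.07 = 13.3, entered on the logit scale. Clinicians with no prior orders get the overall rate.
- **Model statement.** Clinician as the GEE cluster, exchangeable working correlation, robust standard errors. This replaces the reference to clinician random effects, which does not fit a GEE.
- **Reporting.** A standardised risk difference beside the odds ratio, because the odds ratio becomes conditional on the baseline rate.

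The cost is small: one derived variable, a rule for sparse or new clinicians, and that change in the meaning of the odds ratio. A 12-month window may include older behaviour. At the volumes assumed, it still explains more than a perfectly stable 3-month window provided its correlation with trial behaviour exceeds √(0.059/0.163) = 0.60.

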Aim 2 measures, collected through the EMR, will include patient age, sex, race/ethnicity, type of health insurance (e.g., Medicare, Medicaid, Commercial), address, cancer type, and history of prior tobacco cessation pharmacotherapy. Clinician-level data will be collected by survey led by a separate study funded by this grant and approved by the IRB: site, years in practice, patient panel size, the prevalence of patient smoking in the patient panel, and type of oncologist (medical, radiation, surgical). Additional data will include practice-level data: setting (community vs. hospital-based), urban vs. non-urban location, and health insurance mix.

2. Administration of Surveys and/or Process:

Aim 1. No surveys will be administered as part of this study.

Aim 2. Any surveys used as part of this aim will be submitted to the IRB under a separate study protocol prior to use.

3. Data Management:

To minimize the risk of breach of data and confidentiality, we will use secure, encrypted servers to host the data and conduct the analysis. The Digital Academic Research Transformation (DART) will be the hub for the hardware and database infrastructure that will support the project. DART provides a secure computing environment for a large volume of highly sensitive data, including clinical, genetic, socioeconomic, and financial information. DART requires all users of

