6. Statistical Analysis:

Based on our preliminary data, we anticipate including at least 900 smoking patients (based on prevalence estimate of ~7% among 13,000 patients screened over a 1-year study period), nested within at least 100 clinicians. Analysis will use the first TUTS order generated for each patient/physician combination. Data are clustered within clinician, and the exchangeable correlation observed from other studies is small (0.07). We calculated power requirements by simulation using Stata 15, assuming a logistic regression model fitted using generalized estimating equations (GEE), and found our sample gives us 80% power to detect 11% improvement in our primary outcome (e.g., from current 34% referral rate to 45%), using a two-sided type 1 error rate of 5%, for planned comparisons between usual care and each individual nudge arm. The effect of the combined nudge arm is expected to be larger than each individually, indicating at least 80% power to detect probable effects for the comparison between usual care and the combined arm.

We have defined our intention to treat (ITT) sample using the coding algorithm that makes intervention possible, irrespective of whether a nudge was delivered or received. Thus, the ITT cohort is comprised of all eligible patients, defined as those who screened positive for tobacco exposure and have completed the two visits in their randomly assigned cluster. Eligible patients may or may not receive the nudge to which they were assigned and may or may not have access to MyPennMedicine; regardless, all eligible patients are analyzed in the ITT sample.

We have patient-level data on all those screened positive for tobacco but who did not complete the subsequent visits with a clinician in our cluster randomization (e.g., patient came for the first visit where the hidden system variable was assigned and never returned). While these patients are not considered eligible for our trial, they are part of the “screened” population, and we can compare them to our eligible patients on available data to assess the generalizability of our sample.

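### The Aim 1 primary model leaves out patient baseline variables already drawn from the EMR, a modest and avoidable loss of efficiency but not a validity flaw

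*Combined protocol and SAP*

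**What the plan says.** Under Study Procedures, Statistical Analysis, all binary Aim 1 outcomes are to be analysed by logistic regression with GEE, with binary terms for clinician prompt and patient prompt. The adjustment set is: "We will also include adjustments for time in months, fixed effects for site, and random effects for clinician". Testing is hierarchical: overall model, then clinician prompt, then patient prompt. The only other patient variable used in Aim 1 is patient-portal access, in a stratified analysis.

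Under Methods, Study Measures, the EMR is named as the source of the Aim 2 patient variables. Their list reads: "will include patient age, sex, race/ethnicity, type of health insurance (e.g., Medicare, Medicaid, Commercial), address, cancer type, and history of prior tobacco cessation pharmacotherapy". The Statistical Analysis section adds patient-, clinician- and practice-level covariates to the Aim 2 model only. No covariate-adjusted sensitivity analysis of the Aim 1 effect is planned.

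Clinicians are the unit of randomisation, and no stratification by cancer type or by past referral rate is described.

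**The concern.** Patient variables that may predict referral will be in the dataset, but the primary model ignores them. With whole clinicians randomised, an arm's case mix depends on which clinicians fall into it. The target population covers medical and gynecologic oncology, so clinicians are likely to differ in the cancers they see. Site terms cannot remove such differences between clinicians at the same site, and the Background reports individual referral rates running from 0% to 100%.

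If cancer type or a similar variable predicts referral, the confidence interval is wider than the collected data require. If the arms turn out visibly different in case mix, any adjustment not written down beforehand will be open to dispute.

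**Working it through.** **Inputs from the documents.** Two-sided 5% error; 34% against 45% referral; ICC 0.07; at least 900 patients and at least 100 clinicians (all from Statistical Analysis). Equal allocation is assumed, as the ratio is not stated. This gives 9 patients per clinician, 25 clinicians and 225 patients per arm, and 50 clinicians and 450 patients on each side of a factorial main effect. The design effect is 1 + 8 × 0.07 = 1.56.

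**The plan's power figure.** The plan "found our sample gives us 80% power to detect 11% improvement in our primary outcome", "for planned comparisons between usual care and each individual nudge arm".
- One arm against usual care: effective n = 225/1.56 = 144 per group, power 48.0%. A GEE simulation (100 clinicians of 9 patients, no month or site terms) gives about 52%.
- Factorial main effect: effective n = 450/1.56 = 288 per side, power 77.3%; simulation gives about 79%.

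The stated 80% therefore does not reproduce for the comparison it is attached to, but is approached for the main effects that the hierarchy tests. That is a separate matter; it is shown here as the starting point for adjustment.

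**Gain for a general prognostic strength.** R² is the assumed share of outcome variance explained. The standard error is multiplied by √(1 − R²), and effective n is divided by (1 − R²).

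| R² (assumed) | SE reduction | Power, arm vs usual care | Power, factorial main effect |
|---|---|---|---|
| 0 | 0% | 48.0% | 77.3% |
| 0.02 | 1% | 48.8% | 78.1% |
| 0.05 | 2.5% | 50.0% | 79.3% |
| 0.10 | 5% | 52.2% | 81.4% |
| 0.20 | 11% | 57.0% | 85.7% |

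Reaching 80% needs R² of about 0.07 for the main effect and about 0.53 for one arm against usual care.

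**Illustrative cancer-type case.** Assume that 30% of clinicians see only one group of cancers, the rest see only the other, and referral differs between the groups by d = 10, 15 or 20 points. These are assumptions; the documents give no such figures.
- Between-clinician variance: 0.07 × 0.34 × 0.66 = 0.0157.
- Share of it explained: 0.3 × 0.7 × d²/0.0157 = 13%, 30% or 53%.
- Between-clinician share of the variance of a clinician's mean over 9 patients: 0.07/(0.07 + 0.93/9) = 0.40.
- Reduction in the variance of the effect: 5%, 12% or 22%. Reduction in SE: 3%, 6% or 11%.

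**Chance imbalance in the same case.**
- Factorial main effect, 50 against 50 clinicians: SD of the difference in case-mix share = √(2 × 0.3 × 0.7/50) = 9.2 points. Multiplied by 0.10 to 0.20, the effect shifts by 0.9 to 1.8 points (SD).
- One arm against usual care, 25 against 25: √(2 × 0.3 × 0.7/25) = 13 points, a shift of 1.3 to 2.6 points (SD).

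These are upper values, because each clinician is taken to see one case type only. If clinicians see mixed patients, with a covariate ICC of 0.07 to 0.6, the arm-level shift is √(2 × 0.3 × 0.7 × (1 + 8 × ICC)/225) × d, or about 0.5 to 2.1 points. Site terms could reduce it further.

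**The shift is already inside the standard error.** The unadjusted SE for one arm against usual care is √((0.34 × 0.66 + 0.45 × 0.55)/225 × 1.56) = 5.7 points; with 450 per side it is 4.0 points. The shift makes up 1.3²/5.7² = 5% to 2.6²/5.7² = 21% of the arm-level variance. That is close to the 5% to 22% reduction found above: one loss seen from two sides.

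**On top of a clinician's past referral rate.** The plan includes no such covariate, but it is the obvious competitor. At ICC 0.07, a rate from n earlier orders has reliability n × 0.07/(1 + (n − 1) × 0.07): 0.27 for 5 orders and 0.40 for 9. In 1,500 simulated trials of 100 clinicians, adding cancer type to that rate cut the SE by a further 1.8%, 3.5% or 6.9% with 5 orders, and by 0.2%, 2.0% or 4.7% with 9.

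**The case against.** The strongest reply is that nothing here is an error. The planned analysis is valid without patient covariates, and the gain rests on prognostic strengths that the documents do not report. The outcome is a clinician's decision to sign or cancel an order, and the Background attributes its variation largely to opting out and to clinicians' cognitive biases. Patient variables may therefore explain little of the between-clinician variance. Only cancer type is quantified above, and the top case, in which one binary variable explains 53% of that variance, is generous. One hundred clinicians is also a floor: the target population of about 275 would give about 69 per arm.

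Most of this stands. It limits the size of the point and makes it one of efficiency. It does not remove the point: the variables are already collected, and the proportional SE reduction does not depend on the number of clinicians.

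Three stronger readings are tempting and should be resisted.
- A reader might infer that the primary estimate would be biased, or that the imbalance adds to the reported uncertainty. Under randomisation it does neither.
- A reader might apply the 1.3 to 2.6 points to the tests in the hierarchy. Those are factorial main effects, for which the illustrative range is 0.9 to 1.8.
- A reader might expect adjustment to bring one arm against usual care up to 80% power. That needs R² of about 0.53, far above the range considered here.

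**Conclusion.** The point holds as one of efficiency and prespecification. The Aim 1 model omits patient baseline variables that the study already extracts, and no adjusted analysis of the Aim 1 effect is planned. Nothing in the planned analysis is invalid as a result.

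The likely gain is modest: an SE about 1% to 11% lower, and possibly as little as 0% to 5% if a clinician past rate from 9 orders were also in the model. It matters most for the factorial main effects, where power at the planning minimum is just under 80% and a small gain could bring it to that level. The size rests on the assumed R² range, the assumed 30% share and 10 to 20 point referral difference, equal allocation, and 100 clinicians with 9 patients each. The omission itself rests on no assumption.

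**What to change.** In the Aim 1 part of Statistical Analysis, prespecify a short list of patient covariates for the primary model: grouped cancer type (with the groups named), prior cessation pharmacotherapy, age, sex and insurance type. State a simple missing-category rule.

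Use only values recorded at or before the screening encounter. A cut-off at the nudge visit would be too late. The Study Intervention Phase section sends the patient message once smoking status has been established at screening, ahead of the oncology appointment. Cessation-drug history updated in between could already reflect the message in the two arms that receive it.

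Adding covariates changes a conditional odds ratio, so report covariate-standardised referral rates by arm with cluster-robust intervals; the effect then stays population-averaged. The same edit should settle whether the model is GEE or has clinician random effects, since the section now names both and leaves the target effect unclear. Keep the currently planned model as a sensitivity analysis. A clinician baseline referral rate could be added if it can be extracted from the 3-month baseline period.

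The cost is revised SAP text and a little more analysis work: defining the cancer groups, the missing-value rule and the variance method for standardised rates. No new data or patients are needed.
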